9.2. Final Analyses

Final analyses are for efficacy of both ORR at Day 28 and NRM rate at Day 180. Assuming the information fraction at Interim Analysis 2 is 0.826 (360 subjects complete Day 28), efficacy boundaries in [Table 2](#) will be used; if not, the efficacy boundaries will be regenerated using observed information fraction at Interim Analysis 2.

The test steps are as follows:

- E1: Obtain CMH test statistic on ORR at Day 28 (chi-square test with degree of freedom 1),
- E2: CMH test statistic will be compared with the critical value in Column 7 of [Table 2](#) (final analysis chi-square test critical value),
- E3: If positive on ORR at Day 28, NRM rate at Day 180 will be tested using the Bonferroni method.

Note that if there is substantial over-running at the end of the study (ie, total number of subjects is greater than 446), the final critical value will be adjusted in order to control overall Type I error rate.

The final analyses will be conducted by the sponsor.

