### 9.2.3. Final Analysis of the Primary Analysis

Final analysis will be conducted when approximately 436 subjects have completed Day 180 or withdrew from the study. If the observed normalized test statistic crosses the efficacy boundary, then superiority of itacitinib plus corticosteroids over placebo plus corticosteroids will be claimed. Again, ORR at Day 28 will be tested first, and if positive, NRM mortality at Day 180 will be tested.

Note that if there is substantial over-running at the end of the study (ie, total number of subjects is greater than 446), the method to adjust the final critical value will be provided in order to control overall Type I error rate. In such a scenario, details in implementation the rules will be specified in the Statistical Analysis Plan.

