3.2. Control of Type I Error

For the primary and key secondary endpoints, the overall 1-sided Type 1 error is controlled at 0.025. Early stopping for positive efficacy is permitted in this study. Testing of the primary endpoint will use an alpha-spending approach to control Type I error. Subsequent testing of the key secondary endpoint will control Type I error using the Bonferroni method. See Sections 3.4 and 9 for more details.

No multiplicity adjustment will be applied to other endpoints. For estimation purposes, 95% CIs will be provided for parameter estimates of other endpoints.

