The first interim analysis for futility only will be performed when 112 subjects (25.7% of the planned 436 subjects) have completed the Day 28 visit or withdrew early from study. No alpha will be spent during the first interim analysis. The stopping rule is nonbinding. When the conditional power is < 20%, the sponsor may consider terminating the study if the totality of evidence is warranted. The conditional power is calculated assuming that the estimated treatment effect at the interim analysis is the true effect using the formula (Jennison and Turnbull 1999):

$$\Phi \left(\frac{z}{\sqrt{t(1-t)}} - \frac{z_{\alpha/2}}{\sqrt{1-t}} \right)$$

where Φ is the cumulative distribution function of the observed normalized test statistic z , and t is the information fraction (ie, observed sample at interim divided by the planned total sample size 436); $t = 0.257$ at Interim 1 and $z_{\alpha/2} = 1.96$.

Since CMH test with only 1 stratification factor, aGVHD risk status (standard vs high risk), will be used to test ORR at Day 28, it is thus a chi-square test with degree of freedom equal to 1, that is, $\chi^2_{df=1}$. Taking the square root of the observed CMH test statistic $\chi^2_{df=1}$ will result in normalized test statistic z .

3.4.2. Interim Analysis 2

For Interim Analysis 2, the analysis of both efficacy and futility will use a clinical database cutoff based on when 240 eligible subjects (55.0% of the targeted 436 subjects) have completed the Day 180 visit or withdrew from the study prior to Day 180.

The Hwang-Shih-DeCani alpha spending function with shape parameter -4 (O'Brian-Fleming like boundary) will be used to define upper efficacy boundary for the primary analysis of ORR at Day 28 when approximately 240 eligible subjects reach Day 180 (Hwang et al 1990). Based on enrollment projection, there will be approximately 360 subjects who have completed Day 28.

Table 2 lists efficacy boundary when information fraction (ie, the percentage of subjects) is 0.826 (360 subjects complete Day 28) at Interim 2; if ORR tested at Day 28 crosses the boundary, then the key secondary endpoint, 6-month NRM rate, will be tested by using the Bonferroni method for alpha spending (ie, 0.0125 as compared with 1-sided p-value at both interim and final analyses). By simulation, without considering early stopping for futility, the power of testing 6-month NRM at Interim 2 (with 240 eligible subjects who have completed Day 180) is approximately 0.608.

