QT prolongation	Long QT syndrome
QT prolongation	Long QT syndrome congenital
QT prolongation	Torsade de pointes
QT prolongation	Ventricular tachycardia

APPENDIX D. VARIOUS UPPER EFFICACY BOUNDARIES FOR TESTING DAY 28 ORR AT BOTH INTERIM 2 AND FINAL ANALYSES USING HWANG-SHIH-DECANI ALPHA SPENDING FUNCTION WITH SHAPE PARAMETER -4

No. of Subjects in the Interim 2 Efficacy Analysis Set	Information Fraction at IA2 (Column 1/436)	Efficacy Boundary/Critical Value at Interim 2 (as Compared With Observed Normalized Test Statistic z)	Final Critical Value
410	0.940367	2.062174	2.036718
411	0.942661	2.058304	2.037092
412	0.944954	2.054429	2.037452
413	0.947248	2.050549	2.037794
414	0.949541	2.046665	2.038117
415	0.951835	2.042776	2.038417
416	0.954128	2.038882	2.038691
417	0.956422	2.034984	2.038935
418	0.958716	2.03108	2.039144
419	0.961009	2.027172	2.039312
420	0.963303	2.023259	2.039433
421	0.965596	2.019341	2.039498
422	0.96789	2.015418	2.039497
423	0.970183	2.01149	2.039418
424	0.972477	2.007557	2.039247
425	0.974771	2.003619	2.038963
426	0.977064	1.999677	2.038541
427	0.979358	1.995729	2.037951
428	0.981651	1.991776	2.037147
429	0.983945	1.987817	2.036068
430	0.986239	1.983854	2.034627
431	0.988532	1.979885	2.03269
431	0.990826	1.975912	2.030039
433	0.993119	1.971933	2.026284
434	0.995413	1.967948	2.020608
435	0.997706	1.963959	2.010698

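### If Interim 2 does not cross and the study ends with 437 to 446 subjects, the final ORR critical value stays unadjusted and one-sided type I error slightly exceeds 0.025

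*SAP*

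**What the plan says.** SAP 3.2 commits to strong control: for the primary and key secondary endpoints "the overall 1-sided Type 1 error is controlled at 0.025". SAP 3.4.2 sets the Interim 2 efficacy boundary for Day 28 ORR with a Hwang-Shih-DeCani spending function, shape parameter -4.

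The information fraction is defined in SAP 3.4.1 as "observed sample at interim divided by the planned total sample size 436". The fractions in Appendix D are likewise interim counts divided by 436. The body of the SAP works with Interim 2 at a fraction of 0.826, on the projection that "there will be approximately 360 subjects who have completed Day 28". Appendix D tabulates only 410 to 435 subjects at Interim 2.

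If the fraction at Interim 2 is not 0.826, SAP 9.2 says "the efficacy boundaries will be regenerated using observed information fraction at Interim Analysis 2". Nothing there brings in the actual final count. Over-running leads to an adjustment only if the "total number of subjects is greater than 446". Protocol 9.2.3 has the same threshold and leaves the method to the SAP, but SAP 9.2 says only that the value will be adjusted and gives no method.

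**The concern.** In a two-look design, the final critical value depends on the alpha already spent and on the correlation between the two test statistics. That correlation is the square root of the Interim 2 count over the final count. A final count above 436 lowers the correlation, so the final look offers a more independent second chance to reject, and the critical value must rise to hold the same total alpha. The SAP lets the count rise by up to ten with no change.

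The tolerance matters little when 76 planned subjects follow Interim 2 (436 - 360). It matters more when only 1 to 26 follow (436 - 435 to 436 - 410), because ten more then form a large share of the new information. At stake is the decision boundary of the primary endpoint, which is also the gate to testing NRM at Day 180 (SAP 9.2, step E3).

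**Working it through.** **Inputs.** One-sided alpha 0.025 (SAP 3.2). Hwang-Shih-DeCani spending, shape -4 (SAP 3.4.2). Planned total 436 (SAP 3.4.1). Interim 2 sizes 360 (SAP 3.4.2, Table 2) and 410 to 435 (Appendix D). Over-running threshold 446 (SAP 9.2). Futility gets no credit, because the stopping rule is nonbinding (SAP 3.4.1).

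**Formulas.** With n1 the Interim 2 count, t = n1/436 and N the final count:

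- Alpha spent at Interim 2: a(t) = 0.025 (1 - e^(4t)) / (1 - e^4).
- Interim boundary c1: P(Z1 > c1) = a(t).
- Final boundary c2 as planned: a(t) + P(Z1 < c1, Z2 > c2) = 0.025, with corr(Z1, Z2) = sqrt(n1/436).
- Type I error with over-running: the same c1 and c2, but corr(Z1, Z2) = sqrt(n1/N).

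**Reproducing the plan.** At t = 0.826, a(t) = 0.01223, c1 = 2.24981 and c2 = 2.01548, which agree with Table 2 (2.249810 and 2.015483). For Appendix D:

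| n1 | c1 / c2 recomputed | c1 / c2 printed |
|---|---|---|
| 410 | 2.062174 / 2.036718 | 2.062174 / 2.036718 |
| 420 | 2.023259 / 2.039434 | 2.023259 / 2.039433 |
| 430 | 1.983854 / 2.034633 | 1.983854 / 2.034627 |
| 435 | 1.963959 / 2.010564 | 1.963959 / 2.010698 |

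The printed values are therefore sound for a final count of 436.

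**One case in full, n1 = 420.** Alpha spent at Interim 2 is 0.021523. With N = 436 the correlation is sqrt(420/436) = 0.9815 and the final look adds 0.003477, total 0.0250. With N = 446 the correlation is sqrt(420/446) = 0.9704 and the final look adds 0.004482, total 0.026005. A simulation of 20 million draws gave 0.02500 and 0.02602.

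**All cases, final value left unadjusted, and the value that would restore 0.025:**

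| Interim 2 n | c2 at 436 | Type I error, N = 440 | Type I error, N = 446 | c2 required, N = 440 | c2 required, N = 446 |
|---|---|---|---|---|---|
| 360 | 2.015 | 0.0251 | 0.0253 | 2.018 | 2.022 |
| 410 | 2.037 | 0.0253 | 0.0258 | 2.047 | 2.062 |
| 420 | 2.039 | 0.0254 | 0.0260 | 2.056 | 2.078 |
| 430 | 2.035 | 0.0257 | 0.0264 | 2.070 | 2.113 |
| 435 | 2.011 | 0.0261 | 0.0271 | 2.105 | 2.193 |

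At N = 436 every row gives 0.0250. The last row is the extreme of the table: one planned subject after Interim 2 and eleven actual ones.

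**The case against.** The best defence is that this is a deliberate tolerance. Both documents foresee over-running, commit to adjust for it when it is substantial, and give the same numeric threshold, about 2.3% above plan (10/436). The effect inside that tolerance is small. Take the SAP 3.3 rates in two equal strata (68% and 44% against 81% and 61%) with 223 per arm. The standard error of the difference is sqrt((0.1959 + 0.2320)/223) = 0.0438, where 0.1959 and 0.2320 are the mean within-stratum variances p(1 - p) of the two arms. One extra responder then moves z by about (1/223)/0.0438 = 0.10. The missing correction at N = 446 is 0.025 (Interim 2 at 410), 0.039 (420) and 0.079 (430), less than one responder in each case. Only at 435 (0.18) is it more. All of this stands as a statement of size. It does not make the rule consistent with a stated 0.025, and the tolerance was not revisited when Appendix D added late Interim 2 sizes.

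A second defence is futility. If the Interim 2 futility rule were always followed, type I error at N = 446 would be about 0.0233 (360), 0.0246 (410), 0.0250 (420), 0.0254 (430) and 0.0255 (435). The rule is nonbinding, so this credit cannot be claimed, and it would not suffice at the latest sizes anyway.

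A reader might also infer that the SAP now expects Interim 2 at 410 to 435. There is some support: the cutoff fell on 17 APR 2019 (SAP 5.3.2), Amendment 1 is dated 23 JUL 2019 (SAP 10, Table 8), and the appendix added then has no row for 360. But the SAP body still projects about 360, and SAP 10.2.1 presents the Appendix D rows only as further boundaries that might apply. Neither document states the expectation.

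**Conclusion.** The point holds in conditional form. Inflation needs both that efficacy is not declared at Interim 2 and that the final total is 437 to 446. It is then slight. At N = 446, type I error is 0.0253 on the SAP body's projection and 0.0258 to 0.0264 for Interim 2 at 410 to 430. That is 1% to 6% above 0.025 in relative terms, and the extreme row at 435 is 8% above. At N = 440 and Interim 2 at 360 to 430 it is 0.0251 to 0.0257.

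Two stronger readings are not supported. The plan does not fail to control type I error in general: at 436 it is 0.025, and neither document says that over-running has happened or is expected. Nor are the printed boundaries miscalculated: Table 2 and Appendix D reproduce.

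The figures assume that information is proportional to subject count, that the two normalized statistics are jointly normal, that futility earns no credit, and that the final count is not chosen in light of unblinded results. A small defect in the primary decision rule is still worth closing, because a final z between 2.039 and 2.078 (Interim 2 at 420, final 446) would be declared significant although the spending plan does not allow it.

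**What to change.** Delete the 446 threshold from SAP 9.2 and Protocol 9.2.3. In its place state: the final critical value for Day 28 ORR is computed from the alpha remaining after Interim 2 and a correlation equal to the square root of the Interim 2 count over the actual final count, whatever the final count is. Keep Appendix D, labelled as the illustration for a final count of 436. This also supplies the method that Protocol 9.2.3 leaves to the SAP.

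The cost is a wording change and one recalculation, with no new subjects or data. If the study over-runs, the hurdle is higher: 2.062 instead of 2.037 (Interim 2 at 410, final 446), or 2.078 instead of 2.039 (420, 446). If it ends below 436, the same rule gives a slightly lower value, which the text should say openly.

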10. CHANGES AND MODIFICATIONS TO THE ANALYSIS PLAN

All versions of the SAP are listed in [Table 8](#).

Table 8: Statistical Analysis Plan Versions

SAP Version	Date
Original	14 MAY 2018
Amendment 1	23 JUL 2019

10.1. Changes to Protocol-Defined Analyses

Note that the FAS population is equivalent to the efficacy evaluable population as defined in the protocol.

10.2. Changes to the Statistical Analysis Plan

10.2.1. Original to Amendment 1

The Type 1 error control approach for the key secondary endpoint tested at Interim Analysis 2 and the Final Analysis was modified to use the Bonferroni method. Portions of Sections 3 and 9 were modified to reflect that change. In addition, the definition of endpoint for and analysis of Month 6 NRM was refined to reflect Health Authority feedback.

- Section 2 was updated to align with Protocol Amendment 4.
- Section 3 was revised [REDACTED] to provide detail on the interim and final analyses. Figures were added to help visualize the study design and analyses, and the schedule of assessments tables were updated according to Protocol Amendment 4.
- Section 4 was updated to provide additional clarification and definitions.
- Section 5.3 was updated to add the analysis sets used at Interim Analyses 1 and 2. “FAS” replaced “efficacy evaluable population,” and the definition of per protocol analysis set was refined.
- Section 6 was updated to provide clarification and more details on analyses. Disease history was updated according to the current approved CRF, and sections were added for allo-HSCT history and transfusions.
- Section 7 was revised to provide additional clarification and details on efficacy analyses. Alternative ways of calculating DOR were added. Subgroup analyses by [REDACTED], [REDACTED], aGVHD status determined after randomization, MacMillan age group, HLA/donor source category, aGVHD status determined after randomization, and Day 28 response status were added. Timing of 12-, 18-, and 24-month analyses was specified.
- Section 8 was updated for clarification and to add TEAE in the retreatment phase, AE Grade 5, and more AE summaries. The clinically notable AEs were rewritten based on customized MQs. Analyses for EBV in post-transplant lymphoproliferative disorder evaluation were also added.
- Section 9.1 was edited to correct the conditional power formula and to provide more clarification on analyses at Interim Analysis 2.
- [Appendix A](#) was added.
- [Appendix B](#) was updated to redefine TFLs.
- [Appendix C](#) was updated to redefine customized MQs.
- [Appendix D](#) was added for other possible efficacy boundaries for testing Day 28 ORR at both the Interim 2 and final analyses.

In addition, other minor, administrative changes have been incorporated throughout the SAP and are noted in the redline version of the amendment.

APPENDIX A. STATISTICAL MODELS FOR EFFICACY ANALYSES

Analysis for Overall Response

Cochran-Mantel-Haenszel test

The null hypothesis of equality of response rate in the 2 treatment groups will be tested against 1-sided alternative. The statistical hypotheses are:

$$H_0: \text{ORR}_{\text{trt}} \leq \text{ORR}_{\text{pbo}} \text{ versus } H_1: \text{ORR}_{\text{trt}} > \text{ORR}_{\text{pbo}}$$

where ORR_{trt} is the probability of response in treatment group and ORR_{pbo} is the probability of response in placebo group. The CMH chi-square test X2CMH (implemented again via SAS procedure FREQ with CMH option in the TABLES statement) will be used to test the difference in response rates between the treatment groups. The p-value corresponding to the CMH test for “general association” will be used, which follows a Chi-square distribution with 1 degree of freedom.

If the sampling assumptions for chi-square test is not met, the exact CMH test will be used (implemented via SAS procedure MULTTEST). The test is performed by running a stratified version of the Cochran-Armitage permutation test (Armitage et al 1969). In studies with stratified randomization, the chi-square approximation is considered appropriate for the X2CMH statistics if the rule of Mantel and Fleiss (1980) is satisfied.

Logistic Regression

Odds ratio will be used as a measure of association between treatment and response. The odds ratio will be derived from the logistic regression model (implemented using SAS procedure LOGISTIC, with both treatment and stratification factor specified as an explanatory variable in the CLASS statement), which allows for including not only the stratification factor but also for adjustments for other covariates (both categorical and continuous). The odds ratio will be presented with 95% Wald confidence limits.

In cases where an exact test has been used to compare response rates, the odds ratio should be determined using exact logistic regression, and the odds ratio presented with exact 95% confidence limits. In these cases, SAS PROC LOGISTIC with EXACTONLY option will be used.

Analyses for Survival Data

Analyses for Survival Data in this section use OS as an example.

Stratified Log-Rank Test

The null hypothesis stating that OS distributions of the 2 treatment groups are equivalent will be tested against 1-sided alternative

Assuming proportional hazards for OS, the following statistical hypotheses will be tested:

$$H_{02}: \theta_2 \geq 1 \text{ versus } H_{A2}: \theta_2 < 1$$

where θ_2 is the OS hazard ratio (treatment versus placebo). The analysis to test these hypotheses will consist of a stratified log-rank test at an overall 1-sided 2.5% level of significance. The stratification will be based on the randomization stratification factors (ie, aGVHD high vs standard).

The stratified log-rank test adjusting for the strata used in the randomization will be implemented as follows: In each of the K strata separately, the LIFETEST procedure with **STRATA** statement including only the treatment group variable and with the TIME statement will be used to obtain the rank statistic S_k and variance $\text{var}(S_k)$ where $k=1, 2, \dots, K$. The final test statistics will then be reconstructed as follows:

$Z = [S_1 + \dots + S_K] / \sqrt{[\text{var}(S_1) + \dots + \text{var}(S_k)]}$. One-sided P-value will be obtained from the standard normal distribution using the Z statistic.

(One-sided will be obtained using Z statistic / Two-sided p-value will be obtained using Z^2 statistic.)

Kaplan-Meier Estimates

An estimate of the OS survival function in each treatment group at distinct event times will be constructed using KM (product-limit) method as implemented in PROC LIFETEST with METHOD=KM option. The PROC LIFETEST statement will use the option CONFTYPE=LOGLOG. Stratification factor (high vs standard) will be use in **STRATA** statement to get KM estimates by both treatment group and stratum.

Median survival for each treatment group will be obtained along with 95% CIs calculated from PROC LIFETEST output using the method of ([Brookmeyer and Crowley 1982](#)). Kaplan-Meier estimates of the survival function with 95% CIs at specific time points will be summarized. The standard error of the KM estimate will be calculated using Greenwood's formula ([Collett 1994](#)).

Hazard Ratio

Hazard ratio will be estimated by fitting the Cox proportional hazards model using SAS procedure PHREG.

A stratified unadjusted Cox model will be, that is, the MODEL statement will include the treatment group variable as the only covariate and the **STRATA** statement will include stratification variable(s).

Hazard ratio with 2-sided 95% CI will be based on Wald test.

The above survival analyses (ie, log-rank test, KM method and Cox proportional hazards model) do not consider competing risk to be an issue.

Table No.	Title	Population	Standard	In-Text
2.2.31	Cox Regression Analysis of Overall Survival	FAS		X
████	██	████		█
████	██	████		█
2.2.34	Summary of Post-Transplant Lymphoproliferative Disorder Assessment	FAS		X
2.2.35	Summary of ECOG Status in the Treatment Phase	FAS		X
2.2.36	Summary of Death	FAS		X
2.2.37	Summary of Relapse of Underlying Hematologic Disease	FAS		X
Exposure				
3.1.1	Summary of Itacitinib Dose Modifications in the Treatment Phase	Safety		X
3.1.2	Summary of Corticosteroid Exposure Prior to Day 1	Safety		X
3.1.3	Summary of Corticosteroid Exposure in the Treatment Phase	Safety		X
3.1.4	Summary of Corticosteroid Exposure Between Day 1 and Start of New Anti-GVHD Therapy	Safety		X
3.1.5	Summary of Corticosteroid Use Over Time in the Treatment Phase	Safety		X
3.1.4.1	Summary of Itacitinib/Placebo Exposure and Compliance in the Treatment Phase	Safety		X
3.1.4.2	Summary of Itacitinib/Placebo Exposure and Compliance in the Treatment Phase by Age Group	Safety		X
3.1.4.3	Summary of Itacitinib/Placebo Exposure and Compliance in the Treatment Phase by Sex	Safety		X
3.1.4.4	Summary of Itacitinib/Placebo Exposure and Compliance in the Treatment Phase by Race	Safety		X
3.1.4.5	Summary of Itacitinib/Placebo Exposure and Compliance in the Treatment Phase by Region	Safety		X
Adverse Events				
3.2.1.1	Overall Summary of Treatment-Emergent Adverse Events in the Treatment Phase	Safety	X	X
3.2.1.2	Overall Summary of Treatment-Emergent Adverse Events in the Treatment Phase by Age Group	Safety	X	X
3.2.1.3	Overall Summary of Treatment-Emergent Adverse Events in the Treatment Phase by Sex	Safety	X	X
3.2.1.4	Overall Summary of Treatment-Emergent Adverse Events in the Treatment Phase by Race	Safety	X	X
3.2.1.5	Overall Summary of Treatment-Emergent Adverse Events in the Treatment Phase by Region	Safety	X	X
3.2.2	Summary of Treatment-Emergent Adverse Events in the Treatment Phase by MedDRA System Organ Class and Preferred Term	Safety	X	X
3.2.3	Summary of Treatment-Emergent Adverse Events in the Treatment Phase by MedDRA Preferred Term in Decreasing Order of Frequency	Safety	X	X
3.2.4	Summary of Treatment-Emergent Adverse Events in the Treatment Phase by MedDRA System Organ Class, Preferred Term, and Highest Grade	Safety	X	X
3.2.5.1	Summary of Grade 3 or Higher Treatment-Emergent Adverse Events in the Treatment Phase by MedDRA System Organ Class and Preferred Term	Safety	X	X

Table No.	Title	Population	Standard	In-Text
3.2.5.2	Summary of Grade 3 or Higher Treatment-Emergent Adverse Events in the Treatment Phase by MedDRA Preferred Term in Decreasing Order of Frequency	Safety	X	X
3.2.6	Summary of Itacitinib/Placebo Treatment-Related Treatment-Emergent Adverse Events in the Treatment Phase by MedDRA System Organ Class and Preferred Term	Safety	X	X
3.2.7	Summary of Itacitinib/Placebo Treatment-Related Treatment-Emergent Adverse Events in the Treatment Phase by MedDRA Preferred Term in Decreasing Order of Frequency	Safety	X	X
3.2.8	Summary of Itacitinib/Placebo Treatment-Related Treatment-Emergent Adverse Events in the Treatment Phase by MedDRA System Organ Class, Preferred Term, and Highest Grade	Safety	X	X
3.2.9	Summary of Grade 3 or Higher Itacitinib/Placebo Treatment-Related Treatment-Emergent Adverse Events in the Treatment Phase by MedDRA Preferred Term in Decreasing Order of Frequency	Safety	X	X
3.2.10	Summary of Treatment-Emergent Adverse Events With a Fatal Outcome in the Treatment Phase by MedDRA System Organ Class and Preferred Term	Safety	X	X
3.2.11	Summary of Serious Treatment-Emergent Adverse Events in the Treatment Phase by MedDRA System Organ Class and Preferred Term	Safety	X	X
3.2.12	Summary of Serious Treatment-Emergent Adverse Events in the Treatment Phase by MedDRA Preferred Term and in Decreasing Order of Frequency	Safety	X	X
3.2.13	Summary of Itacitinib/Placebo Treatment-Related Serious Treatment-Emergent Adverse Events in the Treatment Phase by MedDRA System Organ Class and Preferred Term	Safety	X	X
3.2.14	Summary of Treatment-Emergent Adverse Events Leading to Itacitinib/Placebo Dose Interruption in the Treatment Phase by MedDRA System Organ Class and Preferred Term	Safety	X	X
3.2.15	Summary of Treatment-Emergent Adverse Events Leading to Itacitinib/Placebo Dose Reduction in the Treatment Phase by MedDRA System Organ Class and Preferred Term	Safety	X	X
3.2.16	Summary of Treatment-Emergent Adverse Events Leading to Discontinuation of Itacitinib/Placebo in the Treatment Phase by MedDRA System Organ Class and Preferred Term	Safety	X	X
3.2.17	Summary of Corticosteroid Treatment-Related Treatment-Emergent Adverse Events in the Treatment Phase by MedDRA System Organ Class and Preferred Term	Safety	X	
3.2.18	Summary of Corticosteroid Treatment-Related Treatment-Emergent Adverse Events in the Treatment Phase by MedDRA Preferred Term in Decreasing Order of Frequency	Safety	X	
3.2.19	Summary of Corticosteroid Treatment-Related Treatment-Emergent Adverse Events in the Treatment Phase by MedDRA System Organ Class, Preferred Term, and Highest Grade	Safety	X	
3.2.20	Summary of Corticosteroid Treatment-Related Grade 3 or Higher Treatment-Emergent Adverse Events in the Treatment Phase by MedDRA System Organ Class, Preferred Term, and Highest Grade	Safety	X	

Table No.	Title	Population	Standard	In-Text
3.2.21	Summary of Corticosteroid Treatment-Related Serious Treatment-Emergent Adverse Events in the Treatment Phase by MedDRA System Organ Class and Preferred Term	Safety	X	
3.2.22	Summary of Treatment-Emergent Adverse Events Leading to Corticosteroid Dose Interruption in the Treatment Phase by MedDRA System Organ Class and Preferred Term	Safety	X	X
3.2.23	Summary of Treatment-Emergent Adverse Events Leading to Corticosteroid Dose Reduction in the Treatment Phase by MedDRA System Organ Class and Preferred Term	Safety	X	X
3.2.24	Summary of Treatment-Emergent Adverse Events Leading to Discontinuation of Corticosteroid in the Treatment Phase by MedDRA System Organ Class and Preferred Term	Safety	X	X
3.2.25	Summary of Treatment-Emergent Adverse Events Leading to Withdrawal From the Study in the Treatment Phase by MedDRA System Organ Class and Preferred Term	Safety	X	X
3.2.26	Overall Summary of Clinical Notable Treatment-Emergent Adverse Events in the Treatment Phase Based on Customized MQs	Safety	X	X
3.2.27	Summary of Clinically Notable Treatment-Emergent Adverse Events in the Treatment Phase Based on Customized MQs by MedDRA Preferred Term and Outcome	Safety	X	X
3.2.28	Summary of Clinically Notable Treatment-Emergent Adverse Events in the Treatment Phase Based on Customized MQs by MedDRA Preferred Term and Highest Grade	Safety	X	X
3.2.29	Summary of Serious Treatment-Emergent Adverse Events in the Treatment Phase by MedDRA System Organ Class, Preferred Term, Hepatic Impairment Status at Baseline, and Postbaseline Azole Usage	Safety	X	X
3.2.30	Summary of Grade 3 or Higher Treatment-Emergent Adverse Events in the Treatment Phase by MedDRA System Organ Class, Preferred Term, Hepatic Impairment Status at Baseline, and Postbaseline Azole Usage	Safety	X	X
3.2.31	Summary of Treatment-Emergent Adverse Events With a Fatal Outcome in the Treatment Phase by MedDRA System Organ Class, Preferred Term, Hepatic Impairment Status at Baseline, and Postbaseline Azole Usage	Safety	X	X
3.2.32	Summary of Itacitinib/Placebo Treatment-Related Treatment-Emergent Adverse Events in the Treatment Phase by MedDRA System Organ Class, Preferred Term, Hepatic Impairment Status at Baseline, and Postbaseline Azole Usage	Safety	X	X
3.2.33	Summary of Grades 3 or Higher Thrombocytopenia Treatment-Emergent Adverse Events in the Treatment Phase by MedDRA System Organ Class, Preferred Term, Hepatic Impairment Status at Baseline, and Postbaseline Azole Usage	Safety	X	X
3.2.34	Summary of Grades 3 or Higher Neutropenia Treatment-Emergent Adverse Events in the Treatment Phase by MedDRA System Organ Class, Preferred Term, Hepatic Impairment Status at Baseline, and Postbaseline Azole Usage	Safety	X	X
3.2.35	Summary of Grades 3 or Higher Anemia Treatment-Emergent Adverse Events in the Treatment Phase by MedDRA System Organ Class, Preferred Term, Hepatic Impairment Status at Baseline, and Postbaseline Azole Usage	Safety	X	X

Table No.	Title	Population	Standard	In-Text
Labs, Vital Signs, and ECGs				
3.3.1	Summary of Laboratory Values – Hematology	Safety	X	X
3.3.2	Shift Summary of Hematology Values – to the Worst Abnormal Value	Safety	X	X
3.3.3	Shift Summary of Hematology Laboratory Values in CTC Grade – to the Worst Abnormal Value	Safety	X	X
3.3.4	Summary of Laboratory Values – Chemistry	Safety	X	X
3.3.5	Shift Summary of Chemistry Values – to the Worst Abnormal Value	Safety	X	X
3.3.6	Shift Summary of Chemistry Laboratory Values in CTC Grade – to the Worst Abnormal Value	Safety	X	X
3.4.1	Summary of Systolic Blood Pressure	Safety	X	
3.4.2	Summary of Diastolic Blood Pressure	Safety	X	
3.4.3	Summary of Pulse	Safety	X	
3.4.4	Summary of Respiratory Rate	Safety	X	
3.4.5	Summary of Body Temperature	Safety	X	
3.4.6	Summary of Body Weight	Safety	X	
3.4.7	Summary of QRS Interval (ms) From 12-Lead ECG	Safety	X	
3.4.8	Summary of QT Interval (ms) From 12-Lead ECG	Safety	X	
3.4.9	Summary of QTcB Interval (ms) From 12-Lead ECG	Safety	X	
3.4.10	Summary of QTcF Interval (ms) From 12-Lead ECG	Safety	X	
3.4.11	Summary of RR Interval (ms) From 12-Lead ECG	Safety	X	
3.4.12	Summary of PR Interval (ms) From 12-Lead ECG	Safety	X	
3.4.13	Summary of Clinically Significant ECG Abnormalities	Safety	X	

Listings

Listing No.	Title
2.1.1	Subject Disposition Status
2.1.2	Subject Enrollment and Site Information
2.1.3	Subject Retreatment Disposition Status
2.2.1	Protocol Deviations
2.2.2	Randomized Subjects With Inclusion/Exclusion Criteria Violations
2.3	Analysis Populations
2.4.4	Demographic and Baseline Characteristics
2.4.5	Medical History
2.4.6	Hematologic Disease History
2.4.7	Prior Anticancer Therapy
2.4.8	Prior Radiotherapy
2.4.9	Prior and Concomitant Medications
2.4.10	Prophylaxis Medications
2.4.11	Conditioning Regimens
2.4.12	PRBC/Platelet Transfusions Performed Within 30 Days Before Enrollment or On Study
2.4.13	Allogeneic Hematopoietic Stem Cell Transplant History
2.5.1	Itacitinib Exposure and Compliance
2.5.2	Corticosteroid Exposure in the Treatment Phase
2.5.3	Corticosteroid Usage After End-of-Treatment
2.6.1	aGVHD Symptoms and Response Assessment
2.6.2	cGVHD Symptoms and Response Assessment
2.6.3	Relapse of Malignant and Nonmalignant Hematologic Diseases
2.6.4	Failure-Free Survival Events and Assessment
2.6.5	Secondary Graft Failure
2.6.6	Acute GVHD Flares
2.6.7	Discontinuation of Immunosuppressive Medication
2.6.8	Post-Transplant Lymphoproliferative Disorder Assessment
████	████████████████████
████	████
2.6.11	Deaths
2.6.12	ECOG Status
2.6.13	PK Blood Sampling Times
2.7.1	Adverse Events
2.7.2	Serious Adverse Events
2.7.3	Grade 3 and Higher Adverse Events
2.7.4	Fatal Adverse Events
2.7.5	Itacitinib/Placebo Treatment-Related Adverse Events
2.7.6	Corticosteroids Treatment-Related Adverse Events
2.7.8	Adverse Events Leading to Itacitinib/Placebo Dose Interruption
2.7.9	Adverse Events Leading to Corticosteroid Dose Interruption
2.7.10	Adverse Events Leading to Itacitinib/Placebo Dose Reduction
2.7.11	Adverse Events Leading to Corticosteroid Dose Reduction
2.7.12	Adverse Events Leading to Discontinuation of Itacitinib/Placebo

Listing No.	Title
2.7.13	Adverse Events Leading to Discontinuation of Corticosteroids
2.7.14	Adverse Events Occurring in the Retreatment Phase
2.8.1	Abnormal Clinical Laboratory Values – Hematology
2.8.2	Clinical Laboratory Values – Hematology
2.8.3	Abnormal Clinical Laboratory Values – Chemistry
2.8.4	Clinical Laboratory Values – Chemistry
2.9.1	Abnormal Vital Sign Values
2.9.2	Vital Sign Values
2.10.1	Abnormal 12-Lead ECG Values
2.10.2	12-Lead ECG Values

